**STATISTICAL ANALYSIS PLAN
FOR**

**Computerized Cognitive Training to Improve Cognition in Diabetic Elderly
Veterans**

(CCT_DEV)

Protocol ID: IIR 11-285

NCT01736124

August 5, 2020

1. Introduction

Diabetes mellitus (DM) has consistently been associated with increased risk for cognitive decline, mild cognitive impairment, and dementia in the elderly. Even minor cognitive impairments in nondemented individuals dramatically affect disease self-management. This, in turn, is associated with poor glycemic and blood pressure control in diabetes, which by themselves increase the risk of dementia, provoking a reinforcing cycle of disease. Thus, it is imperative to find interventions to delay or prevent cognitive compromise in diabetic patients, that can be relatively easily and rapidly implemented, and that are not cost prohibitive. This is especially true in the VA, in view of the high incidence of both diabetes and dementia in the growing population of elderly Veterans.

Epidemiologic evidence suggests modifiable life-style factors, including cognitive activity, may prevent or delay the onset of cognitive decline. Computerized cognitive training (CCT) is an intervention that has shown promising results in the improvement of cognitive functioning, more consistently in non-demented elderly, with additional benefits from booster training sessions. To date, studies of CCT have typically only examined cognitive outcomes, and only shortly after the intervention. The proposed CCT program, Cognifit, is designed to improve cognition of elderly persons by targeting their weak cognitive functions, using a personally tailored training plan. The study will provide an evaluation of the effects of CCT on DM self-management behavior and clinical outcomes, in addition to cognition. Participants for this randomized clinical trial are recruited from the James J. Peters Veterans Affairs Medical Center (VAMC) in the Bronx, NY and the Ann Arbor VAMC (MI).

2. Trial Population

Non-demented DM elderly veterans from the James J. Peters (Bronx, NY) and Ann Arbor (MI) VAMCs have been recruited for this study. Some eligibility criteria are mentioned for screening during the recruitment process.

Inclusion criteria are:

- 55 years old or above
- A diagnosis of type 2 diabetes
- Access to computer and internet
- Identification and provision of contact information of an informant
- Self-management score 18 (of a possible 20) or below on the Diabetes Self-Management Questionnaire (DSMQ)

Exclusion Criteria are:

- Dementia (diagnosis or CDR \geq 1) or prescribed AD medications
- Major medical, psychiatric, or neurological conditions that affect cognitive performance; MMSE <25

- Severe impairment of vision, hearing or fine motor control necessary for computer operation

Eligibility criteria are assessed after potential participants are enrolled by providing signed informed consent at baseline (Visit 1). Following baseline assessment and determination of eligibility, participants are randomized to the CCT intervention, Cognifit, or the active control task. The CCT intervention has games that adapt to the changing performance level of the participant; the active control alternative, has the same games except that they do not adapt to performance, remaining instead at baseline levels. At Visit 2 are introduced to their respective program and are asked perform it 3 days per week (every other day), for 20 minutes, for 24 total sessions. Four months after the intervention, subjects receive a 1-week booster training. Visits 3, 5, and 6 are outcome assessments at the immediate finish of the intervention, six months post-intervention, and 12 months post-intervention, respectively (Figure 1).

[figure not shown]

Figure 1. Timeline of visits from the initial assessments (Month 1; M1) to the final assessments 14 months later.

One of the challenges of internet-based behavior change programs is keeping participants interested and engaged for a sufficient duration, which can be important to ensure a therapeutic benefit. To strengthen participation rates and adherence, staff members call participants once a week, to ask if they are performing the program and if they have any technical difficulties. Nevertheless, we acknowledge that despite these efforts, attrition of subjects occur. Drop out are recorded and Cognifit maintains records, available to this study, of the date and time of each session for each participant in each group.

3. Primary Analysis Objective

The primary outcome measure of this randomized clinical trial (RCT) is the change in DSMQ from baseline (Visit 1) to 6 months after the intervention (Visit 5). The primary analysis is the intent-to-treat (ITT; all enrolled and eligible participants who are randomized) comparison of the two arms of the trial.

4. Analysis Sets/Populations/Subgroups

Intent-to-treat (ITT)

- Differences between the two arms will be assessed among participants with a Clinical Dementia Rating (CDR) score of zero (i.e., excluding those with uncertain dementia [CDR = 0.5]).
- Differences between the two arms will be assessed among participants with and without at least 12 years of education.
- Differences between the two arms will be assessed by sex.

For each seven secondary outcomes, the primary analysis will like the primary analysis for the DMSQ.

For each primary and secondary outcome, a secondary analysis will include the primary covariates to reduce variation attributable to subject differences.

Analyses by CCT Performance

- Group differences between the two arms will be assessed among participants who complete at least 18 of the 24 CCT training sessions as well as the follow-up visit being examined (i.e. Visit 3, 5, or 6).
- Total time spent training (across all sessions by the participant) are data calculated by Cognifit and available to the investigators. This will be used to explore whether training time modifies group differences.
- CCT performance scores are calculated at each session by Cognifit using assessment measures that remain constant regardless of any changes for the participant. For those with at least 18 of 24 trainings sessions, a linear slope will be calculated to explore whether this modifies group differences.

5. Endpoints and Covariates

Endpoints

The primary endpoint is the change from baseline DSMQ to Visit 5.

Seven secondary endpoints, also change from baseline to Visit 5 (except for medication adherence), are:

- Memory – averaged from neuropsychological tests standardized using baseline scores:

Logical Memory - Immediate Recall

Logical Memory - Delayed Recall

CERAD Word List Memory – Immediate Recall

CERAD Word List Memory – Delayed Recall

CERAD Word List Memory –Recognition

- Executive function/attention – averaged from neuropsychological tests standardized using baseline scores:
 - Cancellation Test - Letter
 - Cancellation Test – Shape
 - Trail Making Test – A
 - Trail Making Test – B
 - Digit Span - Forward
 - Digit Span - Backward
- Prospective memory
 - Rivermead time-based subtest (Appointment)
- Medication adherence – by change in renewals and refills of diabetes medications between one year before Visit 1 and one year after Visit 3
- Hemoglobin A1c (HbA1c)
- Diastolic blood pressure – measured twice while sitting and at rest with a five minute interval
- Systolic blood pressure – measured twice while sitting and at rest with a five minute interval

Primary covariates

- age
- sex
- years of education
- baseline MMSE

Secondary covariates

- site – Bronx, NY VAMC versus Ann Arbor, MI VAMC
- ethnicity – Non-Hispanic European Ancestry vs. Other
- Cognitive Self-Report Questionnaire
- Geriatric Depression Scale
- Short – Test of Functional Health Literacy in Adults
- Total Training Sessions

Calculating time

Dates of Visits 1 through 6 are recorded and individual CCT training dates are maintained by the Cognifit and available for use. As indicated in Figure 1 (above), pre-specified intervals are targeted for each visit, but actual visits vary due to scheduling

contingencies with participants and staff. Thus, intervals between assessments are determined from days since Visit 1 (baseline assessment).

6. Handling of Missing Values and Other Data Conventions

Missing data will be accounted for using iterative full information maximum likelihood estimation of the relevant model parameters.

A separate three-step procedure will be used for the sixteen neuropsychological test scores at each visit. The first two steps substitute values for missing data and the third step creates derived scores for use in analyses.

The first step is limiting the participants for whom their neuropsychological data at that visit will be analyzed. Although most participants have data on all the variables, others have some missing data. A participant's data for a visit will be analyzed only if there are at most two missing variables of the 16. A participant must have data analyzed at Visit 1, but may have data analyzed after missing other visits.

The second step is creation of a set of complete data for a visit, by substituting values for any missing data. For all neuropsychological tests except Trails A and Trails B, higher scores indicate good cognition. These two tests are multiplied by minus one, reversing them to make them agree with the other tests. For each variable, using the mean and standard deviation (SD) of the non-missing data, z-scores are calculated by $z = (\text{value} - \text{mean}) / \text{SD}$ for participants with data on that variable. Participants with missing data have no z-score; the "mean substitution" strategy would substitute the mean of the z-scores, which is zero by definition. An improved strategy substitutes the mean of the participant's z-scores for the non-missing variables in that cognitive domain (in addition to memory and executive functions/attention, the remaining 5 neuropsychological tests are in a language domain that is not an outcome measure of this RCT). After this substitution, each participant has score, which is transformed back to the original units by $\text{new value} = \text{score} * \text{SD} + \text{mean}$. This returns the z-scores for non-missing observations to their original values, and provides an estimate for a participant with missing data based on the participant's results in the cognitive domain of the variable. The result is a set of new values with no missing data, for every participant with data analyzed for that visit. Note that the means and standard deviations for the new values differ from those of the original incomplete data.

The third step is to create derived scores for each visit from the new values data of that visit, and the mean and SD of the Visit 1 new values. For every visit, $\text{derived score} = (\text{new value} - \text{Visit 1 new value mean}) / \text{Visit 1 new value SD}$. For Visit 1, the derived score is the z-score, but this is not the case for the other visits, since their derived score is not based on the mean and SD of the new values for that visit. By calculating derived scores this same way at every visit, the participant's change score between a pair of visits is the same as the change for the neuropsychological test, after transformation in the same way as both derived scores for that test. At every visit, derived domain scores for memory and executive functions/attention are sums of the relevant derived scores. By calculating domain scores this same way at every visit, domain change scores between a pair of visits are the weighted sums of the respective change scores for the

neuropsychological tests, with weights based on the transformations of the derived scores.

Medication adherence will be measured by the Continuous, Multiple Interval Measure of Medication Gaps (CMG) method. Using the CPRS diabetes medication refill data, we will identify: 1) refills occurring within one year prior to baseline (Visit 1); and, 2) refills occurring within one year after completion of intervention (Visit 3). To calculate pre-intervention and post-intervention continuous medication gap percentages (CMG), cumulative gaps in medication adherence (the sum of the number of days for which each medication was not available, based on refill amounts and dates) will be divided by the total number of days between the first and last medication fill.

For calculation of linear slope of performance scores, a secondary covariate, we will exclude extreme assessment scores (defined here as above or below 2 standard deviations from the mean – calculated excluding the extreme score itself) since such scores are more likely to be spurious than a true reflection of change.

7. Statistical Methodology

Summary of Study Data

Descriptive statistics for all relevant variables will be calculated and examined at baseline and subsequent visits. The memory and executive functions/attention scores will be the derived domain scores after taking account of missing data. Substantially non-normal distributions will be transformed to reduce the influence of extreme values. All continuous variables will be summarized using the following descriptive statistics: *n* (non-missing sample size), mean, standard deviation, median, quartiles, maximum and minimum. The frequency and percentages (based on the non-missing sample size) of observed levels will be reported for all categorical measures. All summary tables will be structured by group.

Statistical Procedures

The analytic procedure to address the efficacy of CCT will use linear mixed models (LMM) procedures to evaluate change from baseline (Visit 1) to six months post-treatment (Visit 5). Models will include time (coefficient estimate β_1), intervention group (coefficient estimate β_2), and the intervention group by time interaction (coefficient estimate β_3) which indicates whether the change in outcome over time differs between the intervention groups, all as fixed factors, and subjects as a random factor.

The model for the primary outcome (DSMQ) or any of the seven secondary outcome variables (*Y*) for subject *i* and visit *j* at time t_{ij} is:

$$Y(t_{ij}) = b_0 + b_1 t_{ij} + b_2 \text{Group}_i + b_3 t_{ij}\text{Group}_i + u_i + e_{ij}$$

where b_s estimate the fixed effects of group and time, *u* is the subject random effect, and *e* is the residual error. If the result of randomization is that there is a significant ($P < 0.05$) discrepancy between the two arms of the RCT on any of the primary covariates,

that covariate will be included in the model. Since this estimate will be valid for the ITT population under the MAR assumption, it will not be biased in favor of groups with greater dropout.

Although hypothesized demonstration of benefit of CCT beyond that of the active control is directional, tests of significance will be a two-sided at the 0.05 level, to test for the possibility that CCT is substantially inferior to the active control.

Similar procedures will be employed to compare the treatment arms on change from baseline to other visits for the all outcomes.

Analysis for medication adherence

In contrast to all other outcome measures, which are assessed at each visit and primarily used to compare Visit 1 to Visit 5, medication adherence is measured only twice the year before Visit 1 and the year after Visit 3. The LMM and model are exactly the same except the two times are Visit 1 and a year after Visit 3 for the particular participant.

Measures to Adjust for Multiplicity, Confounders, Heterogeneity, Etc.

As this study may be considered preliminary to a potential subsequent large-scale multi-site study of CCT throughout the VA, each secondary outcome will be tested at the 0.05 level.

Secondary analyses controlling for primary covariates are described in #4, ITT analysis. With regard to secondary covariates, such as ethnicity, health literacy, or computer experience, if any are unbalanced or correlate with an outcome at $p < 0.05$, it will be used as a covariate in a secondary analysis, to reduce within-group variation.

Subject Disposition & CONSORT Diagram

We will report the number of subjects, in each group and in the aggregate, that reached:

- Screen
- Randomization
- Baseline
- At least one follow-up
- Each follow-up

We will also summarize attrition rate and reasons for discontinuation if we have them.

8. Sensitivity Analysis

Not applicable.

9. Interim Analysis

Not applicable.

10. Rationale for Any Deviation from Pre-Specified Analysis Plan

Not applicable

11. QC Plans

All variables are examined for errors.

12. Programming Plan

Data are maintained in Excel files. Statistical analysis will proceed using SAS 9.4, Stata v13.1 and SPSS.

13. Appendices

Not applicable.

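### Education and sex subgroups are planned as within-stratum arm differences with no interaction test, so their results cannot show whether the training effect differs between strata

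*SAP*

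**What the plan says.** Section 4 lists three subgroup items under the ITT heading.

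- Education: "Differences between the two arms will be assessed among participants with and without at least 12 years of education".
- Sex: "Differences between the two arms will be assessed by sex".
- CDR: the arm difference is assessed only in participants scoring zero ("i.e., excluding those with uncertain dementia [CDR = 0.5"). No analysis of the 0.5 group is planned.

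Section 7 (Statistical Procedures) gives the only model: "Models will include time (coefficient estimate β_1), intervention group (coefficient estimate β_2), and the intervention group by time interaction", with subject as a random effect. It has no subgroup term. Its inferential rule is that "tests of significance will be a two-sided at the 0.05 level". On multiplicity, Section 7 says that "each secondary outcome will be tested at the 0.05 level" and is silent on subgroups.

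Sex and years of education appear elsewhere only in Section 5, as primary covariates for adjustment. Effect modification is named for other variables. Under Analyses by CCT Performance in Section 4, the SAP says of total training time: "This will be used to explore whether training time modifies group differences". It says much the same of the performance slope.

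**The concern.** A question about subgroups is usually whether the effect of training differs between them. The group-by-time-by-subgroup interaction answers that question. Two separate arm comparisons do not: one may reach significance and the other miss it simply because each stratum holds only part of the sample. Adjusting for sex or education as a covariate does not answer it either, because a main effect says nothing about effect modification.

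Followed as written, the plan would put a P value beside each education level and, on the natural reading, each sex, with nothing to show whether the two results differ by more than chance. A report that training helped one sex or education group but not the other would then have no valid support in the prespecified analysis. The SAP describes the study as possibly preliminary to a larger VA trial, so such a report could affect who is recruited next.

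**Working it through.** **Inputs.** From the SAP: two-sided alpha 0.05 (Section 7); two strata for education and, on the natural reading, for sex (Section 4). The SAP states no power, sample size or stratum shares, so there is no figure of its own to reproduce. Assumptions: overall power of 50%, 80% or 90%; splits of 50:50, 80:20 or 90:10; the same true effect and variance in both strata; 1:1 arms.

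**Formulas.** Let θ = 1.960 + z(power) be the expected z-statistic for the arm contrast in the full sample. In a stratum holding share f of participants, the expected z-statistic is θ√f, so its power is

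Φ(θ√f − 1.96) + Φ(−θ√f − 1.96).

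The strata contain different people, so their tests are independent. With stratum powers a and b, P(exactly one significant) = a(1 − b) + b(1 − a).

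**Overall power 80%, split 50:50.** θ = 1.960 + 0.842 = 2.802 and θ√0.5 = 1.981. Each stratum has power 0.508. P(exactly one) = 2 × 0.508 × 0.492 = 0.500.

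**Overall power 80%, split 90:10.** The stratum powers are 0.757 and 0.144. P(exactly one) = 0.757 × 0.856 + 0.144 × 0.243 = 0.683.

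**Range over the assumptions, P(exactly one significant):**

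| Overall power | 50:50 | 80:20 | 90:10 |
|---|---|---|---|
| 50% | 0.406 | 0.441 | 0.468 |
| 80% | 0.500 | 0.608 | 0.683 |
| 90% | 0.466 | 0.627 | 0.738 |

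The range is about 41% to 74%. Unequal strata raise the figure, but it is already 41% to 50% when they are equal. With no effect in either stratum it is 2 × 0.05 × 0.95 = 0.095.

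**Cross-check.** For a two-sample comparison of means with a standardised difference of 0.5, 63 per arm gives 80.1% power and half that sample gives 51.0%, in line with the 0.508 above.

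**Interaction test.** A simulation of one million draws at 80% overall power, with the same effect in both strata, gave a significant interaction at two-sided 0.05 in 4.96% of draws at 50:50 and 5.00% at 90:10. In the same draws, exactly one stratum was significant in 50.0% and 68.3%.

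**Price of the interaction test.** In units of the overall standard error, the standard error of the difference between stratum effects is √(1/f + 1/(1 − f)), which is 2 at 50:50. Suppose the stratum effects differ by as much as the whole overall effect, at 80% overall power. The expected z-statistic is then 2.802 / 2 = 1.401, and power is Φ(1.401 − 1.96) = Φ(−0.559), about 29%.

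**The case against.** The strongest objection is that the SAP never says strata will be compared with each other, and has no rule that declares a subgroup difference when only one is significant. That is correct. A reader might take the 41% to 74% as the false-positive rate of a planned procedure. It is not: it is the chance of a pattern of results that is easily misread. The objection does not remove the gap, because a plan that reports both sides of a split gives the reader no valid way to compare them.

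Second, the wording for sex is looser than that for education and could allow a model with a sex term. This also stands in part. Separate within-stratum analysis is explicit for education and only the natural reading for sex. On either reading no interaction is specified for sex, although Section 4 uses effect-modification language for training time and performance slope.

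Third, a reader might extend the point to CDR, which sits in the same list. The document does not support that. Only CDR = 0 is analysed, so no pair of strata exists in which just one could be significant. The remaining risk there is that a contrast between the CDR = 0 result and the full ITT result is taken as effect modification.

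Finally, the magnitudes rest on power and splits that the SAP does not give. They are illustrative, but the conclusion does not depend on any one choice within the range.

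**Conclusion.** The point holds for education and, on the natural reading, for sex. The SAP assesses arm differences within strata and specifies no test of whether the effect differs between them. Under a common true effect, a split result (one stratum significant, the other not) has a probability of about 41% to 74% for overall power of 50% to 90% and splits from 50:50 to 90:10, with equal variances and 1:1 arms assumed. A single interaction test holds the corresponding error at 5%. The within-stratum results therefore cannot support a claim that training works differently by sex or education.

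The point does not extend to CDR or to the primary ITT comparison, its model or its significance level. It should be corrected because it affects how secondary findings are read, not because the main result is at risk.

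**What to change.** For sex and for education, specify one model each in the full ITT set. To the Section 7 terms add subgroup, subgroup-by-time, subgroup-by-group and group-by-time-by-subgroup. Report the three-way interaction estimate with its 95% CI and P value. Give the stratum estimates with CIs as description only, and state that differing significance between strata will not be read as a differing effect.

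Label the CDR = 0 analysis as a restricted-population analysis, and say that its contrast with the full ITT result is not evidence of effect modification.

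The cost is a few lines of SAP text and four model terms per factor, eight in all. No new data are needed and the primary analysis does not change. The drawback is the low power of the interaction test, so fewer subgroup claims can be made and a non-significant interaction will not establish that the effects are equal. The CI should carry that message.

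### Site is kept out of the primary model of a two-site trial and can enter only a screened secondary analysis; prespecifying site and site-by-time would be a cheap, minor improvement

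*SAP*

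**What the plan says.** SAP section 1 names two recruiting centres. Section 5 states that "The primary endpoint is the change from baseline DSMQ to Visit 5" and places "site – Bronx, NY VAMC versus Ann Arbor, MI VAMC" among the secondary covariates. The primary covariates are age, sex, years of education and baseline MMSE.

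Section 7 (Statistical Procedures) sets out the primary model. It has fixed terms for time, group and the "intervention group by time interaction", plus a subject random intercept: "where b_s estimate the fixed effects of group and time, *u* is the subject random effect, and *e* is the residual error". The interaction b3 carries the treatment effect, "which indicates whether the change in outcome over time differs between the intervention groups". A covariate can join this model only after a significant (P<0.05) "discrepancy between the two arms of the RCT on any of the primary covariates". Site is not one of those covariates.

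The secondary covariates have a different route, given in section 7 under multiplicity, confounders and heterogeneity. If one is unbalanced, or correlates with an outcome at p<0.05, "it will be used as a covariate in a secondary analysis, to reduce within-group variation".

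On missing data, section 6 says "Missing data will be accounted for using iterative full information maximum likelihood estimation of the relevant model parameters", and section 7 rests the validity of the primary estimate on MAR for this model.

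**The concern.** Site is a design factor, known for everyone at entry, and needs no significance test to justify a place in the model. The plan handles it weakly in three ways.

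- **No route into the primary test.** An imbalance in education could bring education into the primary model. The same imbalance in site could not bring site in.
- **A data-driven screen.** Site is judged by imbalance or by correlation with an outcome, and the SAP does not say whether level or change is meant. Across the primary and seven secondary outcomes, site could be adjusted for in some and not in others.
- **The wrong term.** The screened covariate is meant to reduce within-group variation, but no covariate-by-time term is specified. For a treatment effect defined as a difference in change, a main effect alone does little.

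At stake are some precision, the credibility of MAR if dropout has a site pattern, and the consistency of adjustment across outcomes.

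**Working it through.** The SAP gives no sample size, SD, power, dropout rate or site split, so there is no figure of its own to reproduce. Both checks below rest on assumptions.

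**1. Precision, closed form.** Let g be the gap between sites in mean change, in SDs of within-site change, and q the share of participants at one site. The share of the variance of change that site-by-time removes is

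R² = q(1−q)g² / [1 + q(1−q)g²].

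Starting from an assumed 80% power at two-sided 0.05, power becomes Φ[(1.960 + 0.842)/√(1−R²) − 1.960]. With q = 0.5:

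| Gap g (SD) | q(1−q)g² | R² | Power |
|---|---|---|---|
| 0 | 0 | 0% | 80.0% |
| 0.1 | 0.0025 | 0.2% | 80.1% |
| 0.2 | 0.0100 | 1.0% | 80.4% |
| 0.3 | 0.0225 | 2.2% | 80.9% |
| 0.5 | 0.0625 | 5.9% | 82.3% |

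With a 30:70 site split the gains are slightly smaller: R² is 1.9% at 0.3 SD and 5.0% at 0.5 SD.

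**2. Simulation.** The SAP's random-intercept model was fitted by REML to Visits 1 and 5 in 1,500 trials per scenario. Assumptions: 140 participants, sites 50:50, unit variance within site, within-subject correlation 0.5 and no true effect. The SD of change is then √[2(1−0.5)] = 1, so the units match those of step 1. The Monte Carlo error of a mean b3 is about 0.19/√1500 = 0.005.

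*Standard error of b3:*

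| Scenario | No site | Site main effect | Site + site-by-time |
|---|---|---|---|
| Complete data, site gap in level 0.5 SD | 0.1685 | 0.1685 | 0.1686 |
| 20% missing, gap in level 0.5 SD | 0.1844 | 0.1841 | 0.1842 |
| Complete, unstratified, gap in level 0.5 and in change 0.3 SD | 0.1709 | 0.1709 | 0.1696 |

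The subject random intercept already absorbs a constant site difference, so the main effect leaves the SE where it was.

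*Mean b3 (true value 0), gap in level 0.5 SD throughout:*

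| Dropout pattern | Gap in change | No site | Site main effect | Site + site-by-time |
|---|---|---|---|---|
| By site only (10% vs 35%) | 0 | −0.005 | −0.005 | −0.005 |
| By site only (10% vs 35%) | 0.3 | −0.006 | −0.005 | −0.005 |
| By site and arm (10%/10% and 15%/45%) | 0 | −0.033 | −0.008 | −0.007 |
| By site and arm | 0.3 | −0.052 | −0.021 | +0.006 |
| By site and arm | 0.5 | −0.080 | −0.043 | +0.001 |

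Dropout by site alone gives nothing beyond Monte Carlo error. When dropout depends on site and arm together, the bias is 0.033/0.184 = 0.18 to 0.080/0.191 = 0.42 standard errors. Where change also differs by site, a main effect removes only part of it and site-by-time removes the rest.

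*Type I error without site:* 0.043 to 0.054 in scenarios without site-by-arm dropout, and 0.055 to 0.065 with it.

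**The case against.** The strongest reply is that nothing here is wrong in the sense of invalid. Site is a named covariate, the screen would probably bring a material site effect to light in a secondary analysis, and the random intercept already deals with a constant difference between centres. At site gaps in change of 0.1 to 0.3 SD the power gain is under one percentage point. All of this stands, and it limits the point to a minor one. It does not answer the inconsistency across outcomes, or the absence of any route for site into the primary test.

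A reader might infer more than the documents support:

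- **That the primary test gives up substantial precision.** At a 50:50 split, a 10% variance saving needs q(1−q)g² = 0.10/0.90 = 0.111, so g = 0.67 SD. The SAP offers no evidence of such a gap in change, and zero is possible.
- **That dropout differing between centres biases the estimate.** By itself it does not, as shown above. The SAP expects attrition but suggests no site-by-arm pattern.
- **That the centres differ in staff, populations or adherence calls.** The SAP describes weekly calls without distinguishing sites and gives no comparison of their populations.
- **That randomisation ignored site.** The SAP is silent on stratification, but that is commonly left to the protocol. If assignment was unstratified, chance site imbalance is ordinary sampling variation already reflected in the SE, not bias.

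**Conclusion.** The point holds as a minor weakness. The text is clear that site cannot enter the primary model and reaches only a secondary analysis, after a significance screen that may give different answers for different outcomes. Site-by-time would buy from nothing to about 2% of the variance for site gaps in change up to 0.3 SD, and about 6% at 0.5 SD. It would also protect against a bias of about 0.03 to 0.08 SD if dropout depended on site and arm together and site predicted outcome. These sizes rest on the assumed sample size, correlation, site split and dropout rates, none of which the SAP supplies. The primary test is not invalidated by leaving site out.

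**What to change.** In SAP section 7, extend the model for DSMQ and for each secondary outcome with two fixed terms, b4·Site and b5·time·Site, included whatever any imbalance or correlation test shows. The treatment effect remains b3. In section 5, take site off the screened secondary-covariate list. The main effect alone is not enough, because the effect of interest is a difference in change.

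The cost is two sentences of SAP text and about two degrees of freedom, with no gain in precision if change does not differ by site. The change is worth making whether or not randomisation was stratified by site.
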